## 6.3 Populations for Analyses

Populations for purposes of analysis are defined in [Table 6.3-1](#) below.

**Table 6.3-1: Populations for Analyses**

Population	Description
All Enrolled	All participants who signed an ICF and were registered into the IRT.
All Randomized	All participants who were randomized to any treatment arm in the study. Participants are grouped within the All Randomized population by the treatment to which they were randomized.  This is the primary analysis set for demography, protocol deviations, baseline characteristics, and primary efficacy analyses.
All Treated	All randomized participants who receive at least 1 dose of study drug. Participants are grouped within the All Treated population according to the treatment they actually received. This is the analysis set for all safety analyses and study drug administration.
All Treated from Safety Run-in Phase	All enrolled participants who received at least 1 dose of study drug in the Safety Run-in Phase. Participants are grouped within the All Treated from Safety Run-in Phase population according to the treatment and dose level they actually received. This is part of the analysis set for all safety analysis and study drug administration.
All DLT-Evaluable	All participants treated in Safety Run-in Phase who have discontinued due to a DLT or who have received 1 dose of nivolumab and 75% of accumulative doses of abemaciclib or palbociclib of the cycle, and have completed the 4-week DLT period.
All RCB Evaluable	All Treated participants who have an RCB of 0, I, II, or III from both the Safety Run-in Phase and Randomized Phase.

## 7 STATISTICAL ANALYSES

### 7.1 General Methods

Unless otherwise noted, discrete variables will be tabulated by the frequency and proportion of subjects falling into each category, grouped by treatment. Percentages given in these tables will be rounded to the first decimal and, therefore, may not always sum to 100%. Percentages less than 0.1 will be indicated as '< 0.1'. Continuous variables will be summarized by treatment group using the mean, standard deviation, median, minimum, and maximum values.

Time-to-event variables (e.g. time-to resolution) will be analyzed using the Kaplan-Meier technique. When specified, the median will be reported along with 95% CI using Brookmeyer and Crowley method (using log-log transformation for constructing the confidence intervals).

The conventions to be used for imputing missing and partial dates for analyses requiring dates are described in [Section 8](#).

### **7.1.1 Adverse Events, Serious Adverse Events, Multiple events, and Immune-Mediated Adverse Events**

Drug-related AEs are those events with relationship to study drug “Related”, as recorded on the CRF. If the relationship to study drug is missing, the AE will be considered as drug-related.

Serious adverse events consist of AEs deemed serious by the Investigator and flagged accordingly in the CRF and clinical database.

Adverse events leading to study drug discontinuation are AEs with action taken regarding study drug(s) = “Drug was discontinued”.

Adverse events that led to dose interruption of the drug will be coded with action “Drug was interrupted”.

Adverse events that led to dose omission of the drug will be coded with action “Dose was omitted”.

Adverse events leading to dose reduction are AEs with action taken regarding study drug(s) = “Dose was reduced”.

Adverse events will be coded using the Medical Dictionary for Regulatory Activities (MedDRA), and the most recent version of the dictionary at the time of the database lock will be used. Adverse event results will be graded for severity using the NCI Common Terminology Criteria for Adverse Events (CTCAE) and the version of the criteria specified in the protocol will be used.

In the AE summary tables, unless otherwise specified, subjects will be counted only once at the Preferred Term (PT), only once at the System Organ Class (SOC), and only once at subject level for the counting of total number of subjects with an AE. The AE tables will be sorted by the SOCs and then PTs. SOC will be ordered by descending frequency overall and then alphabetically. PTs will be ordered within SOC by descending frequency overall and then alphabetically. The sorting will be done based on the ‘Any Grade’ column of the experimental arm when arms are presented side-by-side.

Unless otherwise specified, the AE summary tables will be restricted to on-treatment events regardless of the causality.

Analyses that take into account the multiple occurrences of a given adverse event will be conducted (see [Section 7.6.11](#)). To prepare these analyses, the CRF data will be processed according to standard BMS algorithms in order to collapse adverse event records into unique records based on the preferred term. These data will be presented as the rate per 100 person-years of exposure. These analyses will take into account all on-treatment events (allowing more than 1 event per subject) and the total exposure time. The person-year exposure will be computed as the sum over the subjects’ exposure expressed in years where the exposure time is defined as

- Patients treated in Arm C of randomized phase: (Date of last dose of study treatment - date of first dose of study treatment + 31 days)/365.25, for subject who are off study treatment and were followed for at least 30 days after last dose of study treatment.

- Patients treated in Safety run-in phase and Arm A, B of randomized phase: (Date of last dose of study treatment - date of first dose of study treatment + 101 days)/365.25, for subject who are off study treatment and were followed for at least 100 days after last dose of nivolumab.
- (Last known alive date - date of first dose of study treatment +1)/365.25, for subjects who are still on-treatment or who are off study treatment and were followed less than 30 days in Arm C (or 100 days in Arm A or B) after last dose of study treatment.

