CBC with Differential, Chemistry Panel, and Endocrine Testing	X		X C1-C2			Must be performed within 3 calendar days prior to dosing for all time points, except C1D1, which does not need to be repeated if performed within 7 days prior to the first dose. See Section 9.4.4 (Clinical Safety Laboratory Assessments) for list of laboratory tests.
Efficacy Assessments						
Clinical Breast Examination	X					Clinical breast examination by palpation of breast and axilla.

Table 2-2: On-treatment Pre-surgery (Neoadjuvant) Procedural Outline (Safety Run-in Phase and Randomized Phase; CA2097A8)

Procedure ^a	Neoadjuvant Treatment ^{b,c} Cycle 1-5 (1 cycle = 4 weeks)				Pre-surgery (within 7 days prior to surgery)	Notes ^d
	Day 1	Day 8	Day 15	Day 22		
Breast and Axilla Ultrasound (Preferred) or Mammogram	C2D22 (as clinically indicated)				X	Breast and axilla ultrasound (preferred) or mammogram to be done on C2D22 and within 7 calendar days prior to surgery. Every attempt should be made to image each participant using an identical imaging modality and acquisition protocol for all imaging time points.
Documentation of Actual Breast Surgery	See Notes.					Record actual type of BC surgery (ie, BCS, mastectomy) on day of or within 7 days after surgery.

Table 2-2: On-treatment Pre-surgery (Neoadjuvant) Procedural Outline (Safety Run-in Phase and Randomized Phase; CA2097A8)

Procedure ^a	Neoadjuvant Treatment ^{b,c} Cycle 1-5 (1 cycle = 4 weeks)				Pre-surgery (within 7 days prior to surgery)	Notes ^d
	Day 1	Day 8	Day 15	Day 22		
Study Drug						
Randomization	X					First dose to be administered within 3 calendar days following randomization (for Randomized Phase ONLY).
IRT Drug Assignment	X					Register the visit in the IRT for study drug allocation.

Table 2-2: On-treatment Pre-surgery (Neoadjuvant) Procedural Outline (Safety Run-in Phase and Randomized Phase; CA2097A8)

Procedure ^a	Neoadjuvant Treatment ^{b,c} Cycle 1-5 (1 cycle = 4 weeks)				Pre-surgery (within 7 days prior to surgery)	Notes ^d
	Day 1	Day 8	Day 15	Day 22		
Administer Nivolumab 480 mg (Safety Run-in Cohorts and Arms A and B)	X					To be administered Q4W IV. First dose to be administered within 3 calendar days following randomization. 
 • Randomized Phase: • Arm A and Arm B • Starting at C2D1 for Arm B

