5.1.3 Safety Follow-up Period

Depending on the treatment arms, there may be up to 2 in-person safety follow-up visits. FU1 will occur 30 days from the last dose (± 7 days) of the study treatment (PO or IV; whichever occurs later) for all arms. FU2 occurs approximately 100 days (± 7 days) from the last dose of nivolumab for Safety Run-in participants and Arms A and B in the Randomized Phase.

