7.1.1 Nivolumab Dosing (Safety Run-in Cohorts and Randomized Phase Arms A and B)

Participants are to start nivolumab within 3 calendar days of randomization. Participants will receive nivolumab at a dose of 480 mg as a 30-minute IV infusion for a maximum of 5 cycles (maximum 4 cycles for Arm B).

Doses of nivolumab may be interrupted, omitted, or discontinued, depending on how well the participant tolerates the treatment. There will be no dose escalations or reductions of nivolumab allowed. For Q4W dosing cycles, participants may be dosed within a \pm 3-day window.

If a participant cannot receive nivolumab within a \pm 3-day window, nivolumab must be omitted (skipped) for that cycle. If nivolumab is omitted, the other study medications may continue. If a participant discontinues nivolumab, the entire study treatment (CDK4/6 inhibitor and anastrozole) must be discontinued.

When nivolumab is scheduled to be administered on the same day with palbociclib plus anastrozole, nivolumab dosing should be started > 1 hour after palbociclib plus anastrozole ingestion. If nivolumab can not be given within 3 days of palbociclib plus anastrozole administration for a given cycle, nivolumab must be omitted for that cycle.

Premedications are not recommended for the first dose of nivolumab.

Participants should be carefully monitored for infusion reactions during nivolumab administration. If an acute infusion reaction is noted, participants should be managed according to [Section 7.4.4.3](#) (Treatment of Nivolumab Infusion Reaction).

Instructions for dilution and infusion of nivolumab injection may be provided in the clinical protocol, pharmacy binder, or pharmacy reference sheet. Care must be taken to assure sterility of

the prepared solution, as the product does not contain any antimicrobial preservative or bacteriostatic agent.

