## 6 STUDY PERIODS, TREATMENT REGIMENS AND POPULATIONS FOR ANALYSES

### 6.1 Study Periods

- Baseline period:
  - Baseline evaluations or pre-treatment events will be defined as evaluations or events that occur before the date and time of the first dose of study treatment. Evaluations (laboratory tests, pulse oximetry, vital signs [REDACTED]) on the same date and time of the first dose of study treatment will be considered as baseline evaluations. Events (AEs) on the same date and time of the first dose of study treatment will not be considered as pre-treatment events.
  - In cases where the time (onset time of event or evaluation time and dosing time) is missing or not collected, the following definitions will apply:
    - ◆ Pre-treatment AEs will be defined as AEs with an onset date prior to but not including the day of the first dose of study treatment;
    - ◆ Baseline evaluations (laboratory tests, pulse oximetry, vital signs [REDACTED]) will be defined as evaluations with a date (and time if collected) on or prior to the date of first dose of study treatment.
  - If there are multiple valid observations in the baseline period, then the latest non missing observation will be used as the baseline in the analyses. If multiple observations exist on the latest collection date (and time if collected), the record with the latest data entry date and time will be used. If multiple observations exist on the latest collection date (and time if collected) and data entry date and time, then the first observation is used as baseline, unless otherwise specified.

- ◆ Refer to the study-specific protocol for potential additional baseline evaluations definition such as baseline tumor evaluation, etc.
- Post baseline period:
  - On-treatment AEs will be defined as AEs with an onset date and time on or after the date and time of the first dose of study treatment (or with an onset date on or after the day of

first dose of study treatment if time is not collected or is missing). For subjects who are off study treatment, AEs will be included if event occurred within a safety window of 30 days (or 100 days depending on the analysis) after the last dose of study treatment. No “subtracting rule” will be applied when an AE occurs both pre-treatment and post-treatment with the same preferred term and grade.

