### **7.1.1.3 Immune-Mediated Adverse Events (US Submission)**

In order to further characterize AEs of special clinical interest, analysis of immune-mediated AEs (IMAE) will be conducted. IMAEs are specific events (or groups of PTs describing specific events) that include pneumonitis, diarrhea/colitis, hepatitis, nephritis/renal dysfunction, rash, endocrine (adrenal insufficiency, hypothyroidism/thyroiditis, hypothyroidism, thyroiditis, hyperthyroidism, diabetes mellitus, and hypophysitis), and other specific events, considered as potential immune-mediated events by investigator that meet the definition summarized below:

- those occurring within 100 days of the last dose,
- regardless of causality,
- treated with immune-modulating medication (of note, endocrine AEs such as adrenal insufficiency, hypothyroidism/thyroiditis, hypothyroidism, thyroiditis, hyperthyroidism,

diabetes mellitus, and hypophysitis are considered IMAEs regardless of immune-modulating medication use, since endocrine drug reactions are often managed without immune-modulating medication).

- with no clear alternate etiology based on investigator assessment, or with an immune-mediated component.

The list of MedDRA preferred terms used to identify IMAEs is revisited quarterly and updated accordingly. The preferred terms used for the selection at the time of the database lock by categories will be provided.

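### SAP 7.1.1 uses two different last-dose dates for Arm A/B and run-in exposure, so its rules overlap and can credit unobserved time; the 100-day safety tables also outrun routine AE collection, more so in Arm C

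*SAP*

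**What the plan says.** SAP 7.1.1 defines person-years for the multiple-event rates reported under SAP 7.6.11, in three rules.

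- **Rule 1, Arm C.** Last study treatment minus first dose plus 31 days, for participants off treatment and followed at least 30 days after last study treatment.
- **Rule 2, run-in and Arms A/B.** "Date of last dose of study treatment - date of first dose of study treatment + 101 days)/365.25", for participants off treatment who "were followed for at least 100 days after last dose of nivolumab".
- **Rule 3.** Last known alive date minus first dose plus 1, for participants still on treatment, or off treatment and "followed less than 30 days in Arm C (or 100 days in Arm A or B) after last dose of study treatment".

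No order of precedence is given. SAP 6.1 sets the event window for participants off treatment as "within a safety window of 30 days (or 100 days depending on the analysis) after the last dose of study treatment".

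The protocol times late follow-up from nivolumab. Section 5.1.3 says "FU2 occurs approximately 100 days (± 7 days) from the last dose of nivolumab for Safety Run-in participants" and applies the same timing to Arms A and B; Arm C has no such visit. Under Protocol Table 2-3 and sections 9.2.1 and 9.2.2, events are collected for at least 100 days after last nivolumab in nivolumab-treated groups and for 30 days after last dose in Arm C. Later SAEs believed related to study drug or a protocol procedure must still be reported.

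SAP 7.6 tabulates all treated participants by treatment group. The 100-day window is used for immune-mediated events (7.6.8, defined in 7.1.1.3 as "those occurring within 100 days of the last dose"), other events of special interest (7.6.9), pneumonitis and lung disease (7.6.10), the repeat of the drug-related AE summary (7.6.6) and the medication analyses for immune-mediated events (7.4.3.1).

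**The concern.** Rule 2 tests follow-up from one date and counts exposure from a later one. A participant can pass the test well before the end of the interval that the formula credits. The rate then has a denominator containing days on which no one was looking for events. Rule 3 is tied to the later date, so for Arms A/B the two rules are not complements. Two programmers could each follow the SAP exactly and report different rates.

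The second issue is separate. A table that counts events to 100 days after last study treatment is complete only if events are collected that long. They need not be in any arm, and the shortfall is larger in Arm C. Side-by-side counts of immune and pulmonary events would tend to flatter the control arm.

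**Working it through.** The plan states no person-time total, so there is no figure to reproduce. The rules are applied to a participant treated on schedule, with day 1 as first dose.

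**Inputs**

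- Five 28-day cycles (Protocol 5.1); nivolumab every 4 weeks, so the last dose is on day 1 + 4 × 28 = 113.
- Anastrozole counts as study treatment to the end of Cycle 5 (Protocol 7.1.2), day 5 × 28 = 140.
- FU2 falls 100 ± 7 days after last nivolumab: 113 + 93 = 206 to 113 + 107 = 220, centre 213.
- Assumption: the last known alive date is the FU2 date.

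**Overlap in Arms A/B**

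- Rule 2 needs last contact on or after day 213. It credits 140 − 1 + 101 = 240 days.
- Rule 3 needs last contact before day 140 + 100 = 240. It credits the day of last contact.
- Both apply to any last contact on days 213 to 239.

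| FU2 day | Rule 2 | Rule 3 | Understatement of a constant rate if Rule 2 wins |
|---|---|---|---|
| 206 | not met | 206 | 0 |
| 213 | 240 | 213 | 1 − 213/240 = 11.25% |
| 220 | 240 | 220 | 1 − 220/240 = 8.3% |

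With FU2 uniform over days 206–220, days 206–212 (seven days, mean 209) fall under Rule 3 only and the other eight days are credited 240. Mean credit is (7 × 209 + 8 × 240)/15 = 225.5 days against 213 observed, so the understatement is 1 − 213/225.5 = 5.6%.

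**Cycle 5 nivolumab omitted.** Protocol 7.1.1 says "If nivolumab is omitted, the other study medications may continue". Last nivolumab is then day 1 + 3 × 28 = 85, and FU2 is centred on day 185 (178–192). At day 185 the understatement is 1 − 185/240 = 22.9%. Over the window it is (7 × 181 + 8 × 240)/15 = 212.5 credited against 185 observed, or 12.9%.

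**Participants the rules miss**

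- The off-treatment part of Rule 3 names Arms A, B and C only. A run-in participant off treatment with under 100 days after last nivolumab has no rule. One seen on day 213 falls under Rule 2 alone and is credited 240.
- The schedule of activities gives nivolumab as "Starting at C2D1 for Arm B". An Arm B participant who stops in Cycle 1 has no last nivolumab dose, so Rule 2 cannot be evaluated. With 100 or more days after last study treatment, Rule 3 does not apply either.

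**Event window.** SAP 7.6.11 does not say whether its events use the 30-day or the 100-day window. With 30 days, events would stop at day 170 while Rule 2 person-time runs to day 240.

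**100-day tables**

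| | Window ends | Routine collection required to | Days lacking |
|---|---|---|---|
| Arm C | 140 + 100 = 240 | 140 + 30 = 170 | 70 |
| Arms A/B | 240 | 113 + 100 = 213 | 27 |

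The between-arm difference is 70 − 27 = 43 days.

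**The case against.** The best defence is that the Rule 2 formula is right and one word of its condition is wrong. The formula agrees with the SAP 6.1 window. If the condition also referred to study treatment, Rules 2 and 3 would be complementary for Arms A/B. The protocol's 100 days is a minimum, so longer follow-up is allowed. That explains how the text may have arisen and points to the simplest repair, but the text as it stands still overlaps.

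The size is conditional, and that stands too. SAP section 8 bases last known alive date on all appropriate CRF dates, so FU2 need not be the last contact. Once follow-up reaches 100 days after last study treatment, the overlap and the excess credit disappear.

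The two gaps are narrow. Rule 2 groups the run-in with Arms A/B, so its absence from Rule 3 looks like an editorial omission. An Arm B participant without nivolumab has no dated visit after FU1, so 100 days of follow-up would be unusual.

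A reader might infer three stronger things:

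- **That Arm C is at a 70-day disadvantage.** Arms A/B lack 27 days of the same window, so the difference is 43, and late related SAEs are still reportable in every arm.
- **That 23% is an arm-level bias.** It describes one participant with a particular dosing history, and the documents do not say how often that occurs.
- **That the 100-day exposure window must give way to a 30-day one.** The mismatch does not require it.

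Finally, SAP 4.2.4 refers safety details to a core SAP that is not available here. The absence of a precedence rule is established for these two documents only.

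**Conclusion.** The point holds as a minor defect in descriptive safety output. Arm A/B person-time can be programmed in more than one way. If Rule 2 takes precedence, it credits days that were not observed: 11% understatement of the rate for a completer last contacted on day 213, about 5.6% on average over the FU2 window, and up to 23% for a participant who omits Cycle 5 nivolumab but continues oral drugs. It is zero in Arms A/B if Rule 3 takes precedence, and zero wherever follow-up reaches 100 days after last study treatment. These figures assume on-schedule dosing, FU2 as last contact and a constant event rate.

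The 100-day tables lack 70 days of routine collection in Arm C and 27 in Arms A/B. How many events that loses depends on post-treatment hazards that the documents do not give, so no event count is claimed.

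Efficacy, the 30-day AE tables (7.6.6, 7.6.7) and the 30-day dose-decision summaries (7.10) are untouched. SAP 7.6.11 plans no formal comparison.

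**What to change.** **SAP 7.1.1 and 7.6.11**

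- Use the same anchor in the condition and the formula of Rules 2 and 3. The smallest edit replaces nivolumab by study treatment in the Rule 2 condition.
- Cap person-time at the last date of actual follow-up, count events over the same interval, and state that interval in 7.6.11.
- Make the rules mutually exclusive and name the run-in in Rule 3.
- Apply the 30-day rule to participants who never received nivolumab.

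**100-day tables by treatment group (7.6.8–7.6.10, the repeat in 7.6.6, and the immune-mediated event analyses in 7.4.3.1)**

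- Add a 30-day version for side-by-side reading where none exists. SAP 7.10 already uses that window for these event categories at the dose decision.
- Footnote each arm's collection period, or limit the 100-day version to nivolumab-treated groups. If it is limited, the 27-day shortfall in Arms A/B remains and should still be noted.

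Making 30 days the primary exposure window for all arms is optional. The cost is SAP wording and a few repeat tables, with no new data.

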### **7.1.1.1 Select Adverse Events (EU/ROW Submissions)**

The select Adverse Events (select AEs) consist of a list of preferred terms grouped by specific category (e.g. pulmonary events, gastrointestinal events categories, etc.). AEs that may differ from or be more severe than AEs caused by non-immunotherapies and AEs whose early recognition and management may mitigate severe toxicity are included as select AEs. Categories of select AEs may include subcategories (e.g. adrenal disorders, diabetes, pituitary disorders, and thyroid disorders are subcategories of the endocrine event category).

The list of MedDRA preferred terms used to identify select adverse events is revisited quarterly and updated accordingly. The preferred terms used for the selection at the time of the database lock will be provided by categories/subcategories.

In addition to the frequency and worst severity of select AEs, time-to onset, time-to resolution, and time-to resolution where immune modulating medication was initiated will be analyzed for each specific category/subcategory of drug-related select AEs when applicable.

Further details on the definitions time-to onset and time-to resolution are described in [APPENDIX 1](#).

